## 6.5.1 Physical examination

A complete physical examination will include the examination of general appearance, skin, neck (including thyroid), eyes, ears, nose, throat, lungs, heart, abdomen, back, lymph nodes, and extremities, vascular and neurological. If indicated based on medical history and/or symptoms, rectal, external genitalia, breast, and pelvic exams will be performed.

A complete physical examination will be performed at the screening visits for Part 1 (Visit 1) and Part 2 (Visit 301), and also the end of study Visit 416/499. An abbreviated physical examination will be performed at other in person visits as shown in Table 6-1 and Table 6-2. An abbreviated physical exam will include the examination of general appearance and vital signs (BP and pulse) as well as other examinations based on Investigator discretion.

Information for all physical examinations must be included in the source documentation at the study site. Significant findings that are present prior to signing informed consent must be included in the Medical History part of the patient's CRF. Significant findings made after signing the informed consent which meet the definition of an AE must be recorded on the AE section of the CRF.

#### 6.5.2 Vital signs

Vital signs include BP and pulse measurements and are assessed when a complete or abbreviated physical examination is performed. BP will be measured in the sitting position after 5 minutes of rest using an automated validated device (e.g. OMRON) or a standard sphygmomanometer with an appropriate size cuff on the non-dominant arm. Supine BP instead of sitting BP will be measured in patients who are infants or who cannot sit comfortably. Guidelines for the management of hypotension are provided in Appendix 4.

Vital signs (blood pressure and heart rate/pulse) will be collected at Visit 101, 201 during PK assessment (and unscheduled PK/PD visit if it occurs) at: 0, 30 min, 1 hr, 2 hrs, 3 hrs, 4 hrs, 5 hrs, 6 hrs, 7 hrs, 8 hrs, 9 hrs, 10 hrs, 11 hrs, 12 hrs, 18 hrs, and 24 hours post-dose LCZ696. Vital signs at 11 hrs, 12 hrs and 18 hrs are optional unless the patient physically stays on-site. The 24-hr post dose vital signs will be measured if the patient either stays on-site or returns to the site the next day. The vital signs will be collected in Part 1 and Part 2 of the study as depicted in the assessment schedule (Table 6-1 and Table 6-2).

For Part 2 Age Group 3 patients, starting with the first dose of study medication, vital signs need to be checked for up to 4 hours after the initial study medication dose at each dose level. Patients are to remain in the study site clinic for this 4-hour post-dose Vital Sign monitoring period. Vital signs are to be measured pre-dose (time 0), and post-dose at 0.5, 1, 2, 3 and 4 hours for the initial study medication dose at each dose level.

Clinically notable vital signs for this patient population are defined in Appendix 1.

#### 6.5.3 Height/length, head circumference and weight

Height/length in centimeters (cm) will be measured using a standard device at Visit 1 (Part1 PK/PD- Screening), Visit 199 and/or Visit 299, Visit 301 (Part 2 Efficacy- Prerandomization/Screening), and Visit 416/499 (Week 52/Final Visit). Use of a stadiometer for standing height measurements is recommended.

For patients ≤ 3 years, head circumference in centimeters (cm) is measured at Visit 1 (Part 1 PK/PD-Screening), Visit 199 and/or Visit 299, Visit 301 (Part 2 Efficacy-Prerandomization/Screening), and Visit 416/499 (Week 52/Final Visit).

Body weight (to the nearest 0.1 kilogram [kg] in indoor clothing, but without shoes) is measured at every in-person visit. Body weight during hospitalization is to be recorded only if available as per standard of care. For patients 1 month to < 1 year old, last available study weight measurements will be used to ascertain dose. For patients who are 1 to < 6 years old, weight measurements every 3 months will be used for dose determination. For patients who are  $\ge$ 6 years old, weight measurement every 6 months will be used for dose determination.

## 6.5.4 Laboratory evaluations

Complete laboratory evaluations (hematology, blood chemistry, and urine) as outlined in Table 6-4 are performed in Part 1 at Visit 1 (Screening), Visit 199 and/or 299, and in Part 2 at Visit 301 (Screening), Visit 401 (Randomization), Visit 409 and Visit 416/499 (Week 52/Final Visit). Local laboratory should be used for Visit 1, 199, 299 and 301 for complete laboratory evaluations. Central laboratory should only be used for Visit 301, if local lab is unavailable using unscheduled visit. Central laboratory must be used for Visit 401, 409 and 416/499 for complete laboratory evaluations for all patients. Details on the collections, shipment of samples and reporting of results by the central laboratory will be provided to the Investigators in the laboratory manual. Patient can be randomized based on safety laboratory results from Visit 199/299/301 unless the Investigator feels the need to wait for laboratory results from Visit 401.

Abbreviated safety laboratory evaluation consists of serum sodium, potassium, creatinine, and eGFR. Abbreviated safety laboratories should be performed locally. If the local laboratory is unavailable (either for abbreviated or complete labs), the central laboratory should be used as an unscheduled visit. Abbreviated laboratory evaluations are to be performed at Part 1 PK/PD Visits 101, 201, 103 to 120 (when patient comes to the site for a visit about every three months), 203 to 220 (when patient comes to the site for a visit about every three months), UNS PK/PD; and Part 2 (Efficacy) Visits 402 (Abbreviated labs are optional if considered safe and where patient is not being up-titrated), 403, 404 (optional visit; Abbreviated labs are optional if considered safe and where patient is not being up-titrated), 405, 406, 412, 415 and as an optional assessment at UNS TD, and UNS. For those patients who have Visits 299 and 301 on the same

day (for second PK dose patient) or Visits 199 and 301 on the same day (for the first PK dose only patient), laboratories will be performed only once. Local laboratory results will allow Investigators to proceed with study visit procedures without the need to wait for central laboratory results. The local laboratory results must be recorded in the appropriate CRF. Given limitations of blood volume, the local laboratory assessments will be a priority for urgent medical decision making (including for study drug dose titration).

Local and central laboratory results need not agree in order for the Investigator to qualify a patient for the trial or make a dose titration decision. A patient enrolled in the study based on local laboratory results and subsequently determined to be above an exclusion criteria based on central laboratory results may be continued or discontinued from the study at the discretion of the Investigator. The Investigator should use his/her clinical judgment on how best to manage the study drug dose level in the event a dose titration decision based on a local laboratory results is subsequently found to be discrepant with central laboratory results. If the central laboratory is used, it may take up to 72 hours or more to obtain the results.

For child bearing potential females only, serum pregnancy testing will be performed at Visit 1 (Part 1 PK/PD - Screening), Visit 301 (Part 2 Efficacy- Pre-Randomization/Screening) and Visit 416/499 (Part 2 Week 52/End of Study). Child-bearing potential females (CHBP) are defined as all female patients ≥ 11 years of age and all female patients who are <11 years of age if they are menstruating. Patients with a positive urine/serum pregnancy at any time in the study must be excluded. Urine pregnancy test is analyzed locally and done at all visits on all CHBP female patients (for additional details regarding urine pregnancy testing requirements for visits 407, 408, 410, 411, 413, and 414, please see Table 6-2). Serum pregnancy test will be analyzed centrally (for Visit 416/499) or locally (for Visits 1 and 301). A positive urine pregnancy test should be confirmed with a serum pregnancy test.

Table 6-4 Laboratory examinations

Hematology	Biochemistry	Urine measurements**
Hematocrit	Alanine aminotransferase (ALT)	Specific gravity
Hemoglobin	Albumin (Alb)	рН
Platelet count	Alkaline phosphatase (ALP)	Glucose
Red blood cell count (RBC)	Aspartate aminotransferase (AST)	Protein (Total)
White blood cell count (WBC)	Blood urea nitrogen (BUN)	Ketones
WBC differential	Calcium	Bilirubin
	Magnesium	Urobilinogen
	Phosphate	Hemoglobin (blood)
Red blood cell distribution width (RDW)	Chloride	Leukocyte esterase
Mean corpuscular volume (MCV)	Creatinine*	Nitrite
Mean corpuscular hemoglobin concentration (MCHC)	Glucose	WBC
	Potassium*	RBC sediments
	Sodium*	Hyaline casts

Hematology	Biochemistry	Urine measurements**
	Bicarbonate	Granular casts
	Total bilirubin (TBL)	Waxy casts
	Fractionated bilirubin (if total bilirubin >2x ULN)	WBC casts
	Total protein	RBC casts
	Uric acid	
	eGFR*	

\*Abbreviated laboratory evaluations must include these parameters

Study procedures may be performed without restriction while the central laboratory results are pending. In these cases, the Investigator or his/her designee should review the central laboratory results as soon as they become available to decide on whether any adjustments in the patient's study drug or non-study drug regimen are needed.

Abnormal laboratory values (as defined in Appendix 1) may require additional laboratory evaluations be performed, as judged appropriate by the Investigator. If the laboratory abnormality induces clinical signs or symptoms, or requires therapeutic intervention, then the diagnosis or medical condition must be entered on the AE page of the patient's CRF. If the laboratory abnormality is the primary reason for an unforeseen hospitalization or otherwise fulfills the seriousness category of an AE, then the procedure for rapid notification of SAEs must be followed. Likewise, if the laboratory abnormality leads to discontinuation from the study drug (temporarily or permanently), the patient must be followed until the abnormality resolves or until it is judged to be permanent. This investigation may include continued monitoring by repeat laboratory testing or by performing additional laboratory tests as deemed necessary by the Investigator or the Novartis medical monitor.

A table which provides the maximum, allowable blood-draw volumes by weight can be found in Appendix 6.

There are countries where plasma potassium is used instead of serum potassium for routine clinical care. Plasma potassium can be used instead of serum potassium in this study. Serum potassium thresholds in the study protocol, including those values cited in Appendix 1 and Appendix 5, can be converted to plasma potassium thresholds for the study by subtracting 0.4 mmol/L from the serum potassium threshold (Hartland 1999).

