#### Permitted dose adjustments and interruptions of study treatment 5.5.5

The study drug is up-titrated every 2 weeks as tolerated to target dose (level 4 for Group 1 and 2, and 4x for Group 3) as outlined in (Table 3-5 and Table 3-6) based on the safety monitoring criteria (Table 3-3). Additional safety monitoring will be required for Age Group 3 patients with each initial dose level up-titration. See Appendix 13 for details. Following up-titration, the maximum tolerated or target dose will then be maintained for the duration of the study. Both scheduled and unscheduled visits can be utilized for up-titration/down-titration throughout the study based on Investigator judgment.

For patients who are unable to tolerate the protocol-specified dosing scheme, dose level adjustments and interruptions of study treatment are permitted in order to keep the patient on study drug. The following guidelines should be followed:

- The Investigator should adjust doses of concomitant medications if it is believed that they are the most likely cause of an adverse effect
- If adjustment/elimination of concomitant medications is not possible or does not alleviate the side effects of concern, the Investigator may down titrate to the next lower study drug dose level down (Table 3-5 and Table 3-6) to temporary or permanent discontinuation of study drug
- The patient should be rechallenged with the higher dose when the Investigator feels it is appropriate to do so per the directions provided below in this section
- If the study drug is temporarily or permanently discontinued, then the patient should continue to attend the study visits and be followed until the completion of the study

Patients may be seen at any time for unscheduled visits during the randomized treatment epoch for reevaluation of safety criteria parameters. Study drug dose level adjustments should mainly be based on overall safety and tolerability with focus on a) hyperkalemia; b) symptomatic hypotension; and c) renal dysfunction. Local laboratory assessments of serum sodium, potassium, creatinine, and eGFR (calculated based on the modified Schwartz formula (Schwartz 2009) will be utilized. Refer to Appendices 15, 16, and 17 for treatment guidelines for renal dysfunction, management of hypotension and hyperkalemia, respectively.

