After Visit 406 (12 weeks), patients using the adult formulation will be seen at 12 week intervals. The liquid formulation of study drug (LCZ696/matching placebo or enalapril/matching placebo) and LCZ696 granules have a limited shelf life. Therefore, Visits 407, 408, 410, 411, 413, 414 are visits intended primarily to permit dispensation of study drug for patients who are using blinded liquid enalapril/matching placebo and/or LCZ696/matching placebo granules. Given the burden of traveling to study visits for patients and families, the parent/caregiver can come to the site for dispensation of study drug. If the parent/caregiver comes to the visit without the patient, a telephone call to the patient (≥ 6 years old) can be used in conjunction with the parent/caregiver visit for the visit assessments (all can be performed verbally). Delivery of study drug to the patient can also be used where possible and allowed per local regulations. At these visits (407, 408, 410, 411, 413, and 414), the following assessments are performed: concomitant medications, AE/SAEs, dosage administration record, study medication compliance, endpoint collection (for additional details refer to Table 6-2). Urine pregnancy testing will be done for females of childbearing potential (for additional details see Table 6-2). IRT will be contacted if study medications are dispensed.

Visits 407, 408, 410, 411, 413, 414 are telephone visits for patients using the adult formulation of study drug. The assessments listed for these visits (Table 6-2) can be performed by telephone.

Patients who prematurely discontinue the investigational treatment will remain in the study and should undergo all the assessments illustrated in Table 6-2. If a patient/parent(s)/legal guardian(s) withdraws from participation in the study, refuses to return for study assessments or is unable to do so, every effort should be made to contact them or a knowledgeable informant by telephone and/or other measures to determine the patient's survival status 52 weeks from randomization (Visit 499).

Patients will be contacted for safety evaluations during the 30 days following the last administration of study treatment.

Table 6-1 Part 1 Assessment Schedule

Epoch	Scree ning			Period 1 st Dose Pk	(				Period 2 ond Dose P	K		Pre- Randomizat ion
Visit	1	101	102 (telephone visit)	103 to 120*	UNS PK/PD	199**	201	202 (telephone visit)	203 to 220*	UNS PK/PD	299**	301** (Part 2 Screening)
Week	•	*	•				•	•				up to -3

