### 9.1 Analysis sets

For Part 1: All subjects with at least one dose of study drug will be included in safety analysis set. All subjects with evaluable PK/PD data will be included in the PK/PD data analysis.

For Part 2 (Efficacy), the following populations will be used for the statistical analyses

The full analysis set (FAS) will consist of all randomized patients with the exception for those patients who have not been qualified for randomization and have not received study drug, but have been inadvertently randomized into the study. Following the intent-to-treat principle, patients will be analyzed according to the treatment to which they were assigned at randomization. Efficacy variables will be analyzed based on the FAS as the primary population.

The Safety Population (SAF) will consist of all patients who received at least one dose of study drug and have at least one post-baseline safety assessment. Of note, the statement that a patient had no AEs also constitutes a safety assessment. Patients will be analyzed according to the treatment actually received. The safety population will be used for the analyses of safety variables.

The Per-Protocol (PP) population will be a subset of the FAS which will consist of the patients who do not have major deviations from the protocol procedures in the double-blind study stage. Major protocol deviations will be pre-specified prior to unblinding treatment codes for analyses. This supplemental efficacy population will be used to support the primary analysis results.

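### Section 6.5.4 allows discretionary removal from the study, after randomisation, of children whom the FAS must still rank

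*Protocol*

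**What the plan says.** Where local and central results differ, Protocol Section 6.5.4 provides that a patient enrolled on local values and afterwards above an "exclusion criteria based on central laboratory results may be continued or discontinued from the study at the discretion of the Investigator". It sets no criterion for the choice.

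The same section fixes the timing. "Central laboratory must be used for Visit 401, 409 and 416/499 for complete laboratory evaluations for all patients". "Patient can be randomized based on safety laboratory results from Visit 199/299/301", unless the investigator prefers to wait for the Visit 401 result. On delay: "If the central laboratory is used, it may take up to 72 hours or more to obtain the results". Procedures need not pause while a central result is pending, and Table 6-2 has double-blind drug dispensed at Visit 401.

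Section 9.1 leaves out of the FAS only those randomised patients "who have not been qualified for randomization and have not received study drug, but have been inadvertently randomized into the study".

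Elsewhere, follow-up does not depend on staying on drug. If drug is stopped temporarily or permanently, Section 5.5.5 says "then the patient should continue to attend the study visits and be followed until the completion of the study". Section 6 says "Patients who prematurely discontinue the investigational treatment will remain in the study" and applies the Table 6-2 assessments to them. Section 5.6.2 says that permanent discontinuation of drug, without withdrawal of consent, is not withdrawal from the study.

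**The concern.** A protocol that analyses by intention to treat should not itself authorise ending follow-up of a randomised, dosed child at one person's discretion. The primary endpoint ranks every FAS patient on events and function over 52 weeks. A child removed in the first days still has to be ranked, but on almost no observation time. Patients who leave Part 2 are not replaced (Section 4), and Section 9.7 adds no allowance for dropout.

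**Working it through.** **1. Can the trigger fall after dosing?** Eligibility at Visit 301 rests on local laboratories. The central sample is drawn at Visit 401, where the child is randomised and drug is dispensed. The result may take 72 hours or more, and nothing requires a wait. That the child is already dosed is an inference, since the sentence says only that the patient was enrolled, but it is the ordinary course under these rules.

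**2. Is the child in the FAS?** Section 9.1 excludes a patient only if unqualified *and* undosed. A dosed child fails the second condition and stays in.

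**3. The rules side by side.**

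| Section | Situation | Consequence |
|---|---|---|
| 5.5.5, 5.6.2, 6 | Study drug stopped | Stays in follow-up |
| 6.5.4 | Central value beyond an exclusion limit | May leave the study, at discretion |
| 3.1 | Angioedema | Must leave the study (5.6.2 lists it as a reason to stop drug permanently) |
| 6.5.4 against 5.5.5 and 6.5.7 | Pregnancy | Must be excluded, against stays in follow-up |
| 5.4 | Treatment code broken | Continuation in the trial is assessed |

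**4. What would the analysis use?**
- Section 6 gives anyone who leaves the study early a prompt visit with the final-visit assessments. Under Table 6-2 these include NYHA/Ross, PGIS and PedsQL.
- Section 9.4.3 carries the last post-randomisation NYHA/Ross and PGIS values forward to Week 52.
- The Week 52 survival contact in Section 6 is written for families who withdraw, refuse or cannot return. It does not clearly cover removal by the investigator, and it concerns survival, not worsening heart failure.

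**5. Size.** The inputs are Table 9-2 (worst to best): LCZ696 9, 15, 8.1, 10.0, 57.9%; enalapril 13, 19, 12.2, 11.3, 44.5%; two-sided alpha 0.05 (Section 9.4.2).

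The plan's own figure first. P(LCZ696 better) + ½P(tie) = 0.09×0.065 + 0.15×0.225 + 0.081×0.381 + 0.10×0.4985 + 0.579×0.7775 = 0.5705. The odds are 0.4295/0.5705 = 0.753, as stated.

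The pooled proportions are 0.11, 0.17, 0.1015, 0.1065 and 0.512, and their cubes sum to 0.1427. With n per arm, the tie-corrected null variance is (1 − 0.1427)/12 × 2/n.
- n = 177: SE 0.02841, z = 0.0705/0.02841 = 2.48, power = Φ(2.48 − 1.96) = 69.9%. The plan states about 70%.
- n = 180: power 70.6%.

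Now assume that a fraction f of 360 is removed equally in both arms. Expected Category 1/2 events are 24% on LCZ696 and 32% on enalapril, so the number unobserved is 180 × f × (0.24 + 0.32) = 100.8f. This treats removal as happening within days of randomisation.

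| f | Children | Events unobserved | Power if they contribute nothing | Power if carried forward event-free |
|---|---|---|---|---|
| 1% | 3.6 | 1.0 | 70.2% | 70.4% |
| 2% | 7.2 | 2.0 | 69.7% | 70.3% |
| 5% | 18 | 5.0 | 68.4% | 69.8% |

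The fourth column uses 180(1 − f) per arm. The last column moves the removed children's Category 1/2 share into Categories 3-5 in proportion. As an extreme, if 5% were removed from the LCZ696 arm only and carried forward event-free, the odds would move from 0.753 to 0.733 in favour of that arm.

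**The case against.** **A reader might infer that every other passage keeps such patients in follow-up.** The documents do not support that. Section 3.1 (angioedema), the pregnancy sentence in 6.5.4 and Section 5.4 (code break) also remove patients or leave continuation open. The follow-up rules cited above are written for patients who stop drug, not for children found ineligible on a central result. What stands is a conflict with the general rule.

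**A reader might infer that the primary outcome is lost.** It is truncated and imputed. Section 6 provides the final-visit assessments, and Section 9.4.3 asks for all efforts to obtain Week 52 information, ranking on whatever is available and retrievable. The missing part is later event follow-up and the true Week 52 values.

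**A reader might size the problem from assumed disagreement between laboratories.** That would count children open to the choice, not children removed. Exclusion 12 also attaches its potassium limit to Visit 1 and Visit 301, not to Visit 401. No rate can be derived from the documents.

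**Bias between arms.** Section 6.5.4.3 uses the randomisation value as the central eGFR baseline, so the trigger itself should not depend on arm, and treatment is double-blind and double-dummy. Early tolerability may be visible when the choice is made, but the documents give no reason to expect one-sided removal. Blinding limits differential removal; it does not restore the lost follow-up.

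**The point comes late.** The Amendment 7 rationale says that recruitment closed in January 2021 and that 339 of 375 treated patients had finished or discontinued when the urgent safety measure was issued. Rewording recovers nothing for children already removed. This limits the practical gain but does not make the rule sound.

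It is also fair that Section 6.5.4 later describes the response to central results as adjusting drug regimens. That supports treating the sentence as loose wording, and so supports correcting it.

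**Conclusion.** The concern holds in limited form. Section 6.5.4 permits discretionary removal from the study of a child who may already be randomised, dosed and in the FAS, against the rule in Sections 5.5.5, 5.6.2 and 6. The consequence is early truncation of the primary endpoint, with later Category 1 or 2 events having no clear collection route.

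The size is unknown. Under the assumed 1-5% removal, about 1-5 events go unobserved and categorical power falls by 0.4 to 2.2 points (70.6% to 70.2-68.4%) if those children contribute nothing. It falls by 0.2 to 0.8 points if they are carried forward event-free. With the 375 treated patients in place of 360, the event count is 187.5 × f × 0.56 = 105f, again about 1 to 5. The issue is the integrity of the FAS, not sample size.

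The supplied SAP is a regional one that defers to the main SAP for analysis sets and definitions. The main SAP is not among the documents, so its handling of these children cannot be checked.

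**What to change.** Reword the sentence in 6.5.4 along these lines:

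> If a central result places an enrolled patient beyond an exclusion limit, the investigator's discretion concerns study treatment only. In Part 2, a randomised patient stays in the study, is followed to Week 52 under Section 5.6.2 and Table 6-2 unless consent is withdrawn, and is analysed in the FAS as Section 9.1 defines it.

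Reconcile the related passages at the same time, saying for each whether the patient leaves the study or only stops drug: angioedema (3.1 against 5.6.2), code break (5.4) and pregnancy (6.5.4 against 5.5.5 and 6.5.7).

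Because recruitment is closed, also count and report by arm any patients already removed under this sentence, and seek their retrievable Week 52 status, including Category 1 and 2 events, where consent allows.

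The cost is one sentence plus the reconciliation, and site queries for any children already removed. No visits are added, because the Table 6-2 schedule already applies to patients off drug.
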